3.2 Subject Population

The study population is to be limited to subjects with the ZZ or Z-Null A1AT genotype and a low baseline plasma concentration of A1AT. See Section 4.1 for the entry criteria. The total number of subjects to be treated is expected to be between 2 and 25.

Prospective subjects receiving PAT for A1AT deficiency-related lung disease must forego this treatment for at least 8 weeks prior to treatment dosing to support an adequate wash-out, plus a minimum of 3 months post-study treatment. Time off of PAT (at least 5 months) is not expected to have lasting adverse effects based on discussions with A1AT specialists. Furthermore, data from the A1AT Deficiency Registry Group comparing A1AT deficient patients who never received augmentation versus those who received augmentation showed that patients who received PAT at any time had similar benefits as those who were on PAT continuously (Alpha-1 Registry 1998). In Clinical Protocol No. ADVM-043-01, exogenous protein augmentation could confound measurement of plasma A1AT levels after ADVM-043 treatment. Regardless, at any time after treatment administration, the Investigator, in consultation with the Medical Monitor, may make a determination based on clinical judgment and study data to resume or start PAT. Subjects who resume or start PAT post-treatment will remain in the study and continue to be followed for safety-related parameters according to the schedule of assessments.

3.3 Cohort Size Rationale

The initial cohort size of 2 subjects is to minimize the number of subjects potentially exposed to a sub-therapeutic dose of ADVM-043, which has limited potential for a second administration due to the development of neutralizing antibodies. Furthermore, A1AT deficiency is a rare disease, with a prevalence of about 1 to 5 per 10,000 (NLM 2018). This small population of potential subjects will further be limited by the protocol exclusion criteria, such as the presence of pre-existing neutralizing antibodies to AAVrh.10 and the requirement for the 8-week washout period for subjects on PAT before treatment with ADVM-043. In addition, data from historical clinical trials conducted in A1AT subjects support a low rate of withdrawal from the studies

(Chapman, Burdon et al. 2015), which further supports the initial cohort size of 2 subjects because the likelihood of subjects with incomplete data is predicted to be low.

Treatment-related adverse events (AE) are anticipated to be rare. Other studies investigating liver-directed gene therapies have reported mostly mild AEs, the majority of which were transient asymptomatic transaminitis. [REDACTED]

[REDACTED] an alanine aminotransferase (ALT) measurement of $>2 \times$ upper limit of normal (ULN) will trigger further clinical investigations (Section 13.2). These results will be reviewed closely by Adverum and are to be part of the cumulative safety data review by the DMC prior to a dose-escalation decision.

3.4 Cohort Assignment

In Part A, the first subject assigned to a Cohort will receive a single IV infusion of ADVM-043 at 8×10^{13} vg. Beginning on the day of treatment (Day 0), the subject is to be monitored for safety and treatment effects at protocol-specified study visits. The first subject will be considered a “sentinel” subject and a minimum of 2 weeks (14 days) will separate dosing of the first and second subject within a cohort. There will be a minimum of 4 weeks between dosing of the last subject in one dosing cohort and the first subject in the next dosing cohort which will include a DMC review of the safety and (as appropriate) efficacy data within a dosing cohort.

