3.1 Study Design

Clinical Protocol No. ADV-043-01 is a Phase 1/2, open-label, multicenter, dose-escalation clinical trial to evaluate the safety and treatment effect of ADV-043, an IMP, in subjects with A1AT deficiency. The study is intended to test the hypothesis that administration of ADV-043 (AAVrh.10 vector expressing human A1AT) to individuals with A1AT deficiency is safe and results in persistent potentially therapeutic levels of A1AT in blood and alveolar epithelial-lining fluid (ELF). Subjects are to be treatment-naïve to PAT or to have stopped receiving PAT at least 8 weeks prior to treatment administration (Section 4.1). Therefore, detection of plasma A1AT levels over baseline will provide evidence of activity of ADV-043.

In Part A, ADV-043 is to be administered by intravenous (IV) infusion. In Part B, ADV-043 is to be administered by intrapleural injection. Up to 4 dose-levels are to be tested in Part A (see below) and 1 dose-level in Part B. Safety and efficacy data, including maximum tolerated dose (MTD), from Part A will be considered when determining whether to proceed to Part B and the dose-level to be delivered.

- | | |
|----------|--|
| Cohort 1 | ADV-043 at 8×10^{13} vg
($\sim 1 \times 10^{12}$ vg/kg based on an 80-kg subject) |
| Cohort 2 | ADV-043 at 4×10^{14} vg
($\sim 5 \times 10^{12}$ vg/kg based on an 80-kg subject) |
| Cohort 3 | ADV-043 at 1.2×10^{15} vg
($\sim 1.5 \times 10^{13}$ vg/kg based on an 80-kg subject) |
| Cohort 4 | ADV-043 at 4.8×10^{15} vg
($\sim 6 \times 10^{13}$ vg/kg based on an 80-kg subject) |

Figure 1: Study Schema

In addition to the ADVM-043 study treatment, [REDACTED]

[REDACTED]

Study visits and assessments over 52 weeks post-study treatment will permit monitoring of subject safety and change in A1AT concentration. Upon completion of the End-of-Study Visit (EOS), subjects will be offered enrollment in a long-term follow-up study to further assess the safety and durability of transgene expression.

A Data Monitoring Committee (DMC) will be involved in the study to ensure subject safety. Review of subject safety, including dose-limiting toxicities, will be conducted by the DMC and Adverum before potential dose-escalation to the next treatment cohort. Furthermore, specific safety signals may result in immediate suspension of further dosing and recruitment until a discussion and review of the safety data with the DMC has occurred (Section 3.10).

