3.5 Rationale for dose selection

In Part A, ADVM-043 will be administered IV at 4 dose levels:

ADVM-043 at 8×10^{13} vg

ADVM-043 at 4×10^{14} vg

ADVM-043 at 1.2×10^{15} vg

ADVM-043 at 4.8×10^{15} vg

[REDACTED]

All 4 dose levels for Cohorts 1 through 4 remain below the NOAEL and are expected to be safe, based on the findings from Study ADVM-1701.

[figure not shown]
To date, over 100 clinical trials utilizing AAV driven gene therapy have been conducted (<https://www.wiley.com/legacy/wileychi/genmed/clinical/>). Multiple studies have used or are using similar doses to those being explored in this study. In one such study, doses up to 5.0×10^{12} vg/kg of liver-directed gene transfer for hemophilia B employing the AAVrh.10 vector (AAVrh.10FIX) were found to be generally well tolerated. (Dimension Therapeutics 2017). In a separate hemophilia A study conducted by BioMarin, the dosing of AAV5 (BMN 270) at 6×10^{13} vg/kg (approximately 4.6×10^{15} vg/subject based on the median weight) in 7 subjects has been shown to be safe and well-tolerated, and to produce durable and therapeutic FVIII levels out to 78 weeks (Biomarin 2017). BioMarin is currently conducting a global Phase 3 study in up to 40 subjects with hemophilia A with BMN 270 at 6×10^{13} vg/kg (ClinicalTrials.gov: NCT03370913 2018).

In ADV-043-01, four dose levels have been selected to find a safe dose with the potential to show a meaningful effect in achieving plasma A1AT concentrations at or above the therapeutic target of 0.57 mg/mL (approximately 11 μ M) that could potentially benefit patients with progressive lung disease. At the same time, we want to minimize patient exposure to sub-therapeutic doses of ADV-043 and therefore have selected as low as 2 subjects per cohort (Section 3.3). Normal human A1AT (M-A1AT) levels range from 1.09 to 2.61 mg/mL (20 to 50 μ M).

[REDACTED] A starting clinical dose of [REDACTED] is projected to result in protein expression levels of approximately 0.04 to 0.1 mg/mL of M-A1AT in humans and that the highest dose of [REDACTED] may potentially reach approximately 2.4 to 6.0 mg/mL of M-A1AT in humans if the protein expression between mice and humans was equivalent.

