3.6 Dose-Limiting Toxicity and Maximum Tolerated Dose

The first treated subject in a Cohort will be considered the sentinel subject. The proposed dosing interval is at least 14 days between the sentinel and second subject to be dosed, provided there are no safety concerns in the sentinel subject prior to dosing the next subject.

A dose-limiting toxicity (DLT) is defined as any AE Grade ≥ 3 attributed to ADV-043 and occurring within the DLT observation period. The DLT observation period is based on data from ongoing studies in liver-targeting gene therapy showing that treatment-related adverse events have occurred in general within 4 weeks of study treatment and have not led to long term sequelae (Pasi 2017, Dimension Therapeutics 2017).

The DLT observation period for the sentinel subject is 6 weeks (14 days plus 4 weeks) post study treatment; and for the second or any subsequent subject within the same dosing cohort, 4 weeks post study treatment. This takes into consideration the 14-day minimum interval between the sentinel subject and the second subject dosed in a cohort and the 4-week DLT observation period. The DLT observation period will be used during the review between the DMC and Adverum to make decisions related to dose escalation and cohort expansion. If a subject

withdraws from the study prior to completion of the DLT observation period, the subject will be replaced and followed for DLTs before decisions regarding cohort expansion are made.

Any AE Grade ≥ 3 attributed to ADVM-043 that occurs outside of the DLT observation period will require enrollment suspension until review and assessment of the event has taken place (Section 3.9).

Within each dosing cohort, the first DLT will result in cohort expansion from a total of 2 subjects to a total of 5 subjects. If more than one DLT occurs within the same dose cohort, the MTD will have been exceeded; de-escalation and cohort expansion of the prior cohort or an additional intermediate dose may be considered. The MTD will be the dose at which no more than 1 of the 5 subjects in an expanded cohort experiences a DLT.

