5.0 STUDY TREATMENTS

5.1 Formulation

The biological product ADVM-043 is a genetically engineered, replication-incompetent, adeno-associated viral vector of serotype rh.10 (AAVrh.10), encoding human alpha-1 antitrypsin (A1AT complementary deoxyribonucleic acid (cDNA)). ADVM-043 is [REDACTED]

[REDACTED] Refer to the Investigator's Brochure for additional product details.

Investigational Drug Product

Product Name	ADVM-043
Dosage Form	[REDACTED]
Unit Dose	Part A Cohort 1 ADVM-043 IV at 8×10^{13} vg Cohort 2 ADVM-043 IV at 4×10^{14} vg Cohort 3 ADVM-043 IV at 1.2×10^{15} vg Cohort 4 ADVM-043 IV at 4.8×10^{15} vg Part B Dose for intrapleural injection will be determined from Part A
Route(s) of Administration	Part A intravenous infusion Part B intrapleural injection
Physical Description	Once thawed, ADVM-043 is a clear, colorless liquid

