4.1. Overall Study Design and Plan

Study ADVM-043-01 is a Phase 1/2, open-label, multicenter, dose-escalation, first-in-human study to evaluate the safety and efficacy of ADVM-043 (AAVrh.10 vector expressing human A1AT), an investigational medicinal product (IMP) that is intended to deliver a functional gene to the liver of the subjects with A1AT deficiency.

The study is intended to test the hypothesis that ADVM-043 to individuals with A1AT deficiency is safe and results in persistent potentially therapeutic levels of A1AT in blood and alveolar epithelial-lining fluid (ELF). Subjects enrolled in the study will be treatment-naïve to protein augmentation therapy (PAT) or will have stopped receiving PAT at least 8 weeks prior to treatment administration. Therefore, detection of plasma A1AT levels over baseline will provide evidence of activity of ADVM-043.

In Part A of the study, ADVM-043 will be administered by IV infusion up to 4 dose-level cohorts. In each cohort, ADVM-043 will be initially administered to 2 subjects and may be administered to an additional 3 subjects in each cohort level after review by a data monitoring committee (DMC). Safety and efficacy data, including the maximum tolerated dose (MTD) observed from Part A, will be considered when determining whether to proceed to Part B and at what dose level.

In Part A, the first subject assigned to a cohort will receive a single IV infusion of ADVM-043 at 8×10^{13} vg. Beginning on the day of treatment (Day 0), the subject will be monitored for safety and treatment effects at protocol-specified study visits (Appendix 13.1). The first subject will be considered a sentinel subject and a minimum of 2 weeks (14 days) will separate dosing of the first and second subjects within a cohort. There will be a minimum of 4 weeks between dosing of the last subject in one cohort and the first subject in the next cohort which will include a DMC review of the safety and efficacy data within a dosing cohort.

In Part B of the study, ADVM-043 will be administered by intrapleural injection at 1 dose-level. The Schedule of Assessments is in Appendix 13.1.

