6.8. Study Treatments

ADVM-043 is a genetically engineered, replication-incompetent, adeno-associated viral vector of serotype rh.10 (AAVrh.10), encoding human alpha-1 antitrypsin (A1AT complementary deoxyribonucleic acid (cDNA). Once thawed, ADVM-043 is a clear, colorless liquid.

In Part A of the study, ADVM-043 will be administered by IV up to 4 dose-levels.

- Cohort 1 ADVM-043 at 8×10^{13} vg
- Cohort 2 ADVM-043 at 4×10^{14} vg
- Cohort 3 ADVM-043 at 1.2×10^{15} vg
- Cohort 4 ADVM-043 at 4.8×10^{15} vg

Part B of the study was not continued and will be excluded from this analysis plan.

No subjects were enrolled into Cohort 4 of the study.

ADVM-043 exposure details will be listed by dose cohort and subject.

In Mock Shell: Listing 16.2.5

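### Protocol 3.4 and SAP 4.1 give the first subject of a cohort 8×10^13 vg without limiting this to Cohort 1, which contradicts the cohort dose lists

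*Protocol*

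**What the plan says.** Protocol 3.4 (Cohort Assignment) reads "In Part A, the first subject assigned to a Cohort will receive a single IV infusion of ADVM-043 at" 8×10^13 vg. SAP 4.1 carries the same statement: "the first subject assigned to a cohort will receive a single IV infusion of ADVM-043 at" 8×10^13 vg. Neither names Cohort 1 or the first subject of the study. Both paragraphs then call the first subject the sentinel and set a minimum of 14 days between the first and second subjects of a cohort.

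Other sections confirm that the sentinel is a role in every cohort. Protocol 3.6 says "The first treated subject in a Cohort will be considered the sentinel subject", and the Synopsis gives the sentinel of each dosing cohort a 6-week DLT window.

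The doses are set out by cohort in the Synopsis, in Protocol 3.1 ("Up to 4 dose-levels are to be tested in Part A (see below) and 1 dose-level in Part B"), in the unit-dose table of Protocol 5.1 (for example "Cohort 2 ADVM-043 IV at" 4×10^14 vg) and in SAP 6.8 ("In Part A of the study, ADVM-043 will be administered by IV up to 4 dose-levels"). Protocol 3.5 lists the same four levels. In the by-cohort lists 8×10^13 vg belongs to Cohort 1 alone, and none of them gives the sentinel a separate dose.

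**The concern.** For the sentinel of Cohort 2 or any later cohort, the documents describe two doses: the figure in Protocol 3.4 and the figure in the cohort list. No passage says which governs.

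Three things depend on a single answer:

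- **Escalation.** Protocol 3.7 allows escalation after no DLT in two subjects. That rule presumes that both were treated at the cohort's dose.
- **Overdose and deviation.** Protocol 7.6 defines overdose relative to the dose that the protocol describes, and Protocol 5.2 asks for reasons when administration departs from the expected regimen. Neither can be applied cleanly to a later sentinel while two figures stand.
- **Reporting.** SAP 6 summarises everything by cohort, which presumes one dose per cohort. SAP 4.1 and SAP 6.8 disagree on that.

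**Working it through.** **1. Which cohort does the figure in Protocol 3.4 belong to?** The inputs are the cohort doses and the 80-kg reference weight in Protocol 3.1. Dose divided by 80 kg reproduces the protocol's own per-kg figures exactly. Dividing each listed dose by 8×10^13 vg gives the size of the discrepancy.

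| Cohort | Listed dose (vg) | Dose / 80 kg (vg/kg) | Listed dose / 8×10^13 | 8×10^13 as % of listed dose |
|---|---|---|---|---|
| 1 | 8×10^13 | 1×10^12 | 1 | 100 |
| 2 | 4×10^14 | 5×10^12 | 5 | 20 |
| 3 | 1.2×10^15 | 1.5×10^13 | 15 | 6.7 |
| 4 | 4.8×10^15 | 6×10^13 | 60 | 1.7 |

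The figure in Protocol 3.4 is therefore the Cohort 1 dose.

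**2. Does the context limit the sentence to Cohort 1?** Not explicitly. The paragraph in 3.4 moves from the first subject assigned to a cohort, to that subject as sentinel, to the spacing of first and second subjects within a cohort, to the gap between cohorts. Everything after the dose and monitoring sentences applies to each cohort.

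**3. What would a literal reading do to the two-subject rule?** This is an illustration. The documents give no DLT risk, so a range of p = 0.1 to 0.5 at the listed dose is assumed, with independent subjects and no DLT risk in a sentinel treated at 8×10^13 vg.

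- Both subjects at the listed dose: P(no DLT) = (1 − p)².
- Only the second subject at the listed dose: P(no DLT) = 1 − p.

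In a cohort expanded to five, four rather than five would be at the listed dose. The chance of at most one DLT among n subjects is (1 − p)^n + n·p·(1 − p)^(n−1). It is shown for a fixed n, ignoring the event that triggers expansion.

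| Assumed p | No DLT in pair, both at listed dose | No DLT in pair, sentinel at 8×10^13 | At most 1 DLT, n = 5 | At most 1 DLT, n = 4 |
|---|---|---|---|---|
| 0.1 | 0.81 | 0.90 | 0.919 | 0.948 |
| 0.2 | 0.64 | 0.80 | 0.737 | 0.819 |
| 0.3 | 0.49 | 0.70 | 0.528 | 0.652 |
| 0.4 | 0.36 | 0.60 | 0.337 | 0.475 |
| 0.5 | 0.25 | 0.50 | 0.188 | 0.312 |

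Zero risk in the sentinel is the extreme case. With a sentinel risk q between 0 and p, the pair probability is (1 − p)(1 − q), which lies between the two pair columns.

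**4. Which cohorts could be affected?** SAP 6 and 6.8 state that Cohort 4 was not enrolled and that the study did not go on to Part B. The 60-fold ratio is thus a ratio on paper only. Cohorts 2 and 3 remain.

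**The case against.** The strongest reply is that the sentence was meant for the first subject of Part A, who starts at the lowest level, and that the rest of the documents make this plain. Every by-cohort list gives one dose per cohort. Protocol 3.5 says "In Part A, ADVM-043 will be administered IV at 4 dose levels". Protocol 3.7 sends the next subject after a clean pair to the higher cohort and then speaks of that cohort's sentinel, so that subject is the sentinel there. A fixed sentinel dose would work against the escalation design and against the aim in Protocol 3.3 of limiting sub-therapeutic exposure. Preparation and administration follow an IMP Manual that is not part of these documents. In the SAP the sentence is background: the DLT flag in SAP 5.4.7 and the planned summaries do not draw on it.

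Most of this stands. It makes a drafting slip the likely explanation, and correcting the sentence would change no planned table. It does not remove the contradiction, because the sentence is complete, appears in both documents and is not ranked below the lists by any other passage.

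A reader might go further and infer that a low sentinel dose was planned, or that sentinels in Cohorts 2 and 3 received less than their cohort's listed dose. The documents support neither: no section gives a rationale for a separate sentinel dose, and nothing reports the dose that any subject received.

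**Conclusion.** The contradiction is real and stands in the current text of both documents. The figure in Protocol 3.4 and SAP 4.1 is one fifth of the dose listed for Cohort 2 and one fifteenth of that for Cohort 3, the two later cohorts where it could have had any practical effect.

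The probabilities in the working describe only what would follow if the sentence were obeyed literally. They rest on assumed DLT risks and on zero risk in the sentinel, and they do not measure a flaw in the escalation rule as the protocol otherwise states it. This is a consistency error in a dosing statement, worth correcting because it concerns dosing in a first-in-human study with a single administration. It is not evidence of misdosing or of a defective design.

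**What to change.** Reconcile Protocol 3.4 and SAP 4.1 with the Synopsis, Protocol 3.1, 3.5 and 5.1 and SAP 6.8, so that the documents state one dose per cohort and say explicitly whether it applies to the sentinel. The sponsor must confirm which text is correct; this review does not choose between them.

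The by-subject exposure listing already planned in SAP 6.8 can be used to state in the study report what each sentinel received.

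The cost is one sentence in each document, plus the approval steps in Protocol 11.2.1 if the protocol itself is amended. No planned analysis changes.

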3.5 Rationale for dose selection

In Part A, ADVM-043 will be administered IV at 4 dose levels:

ADVM-043 at 8×10^{13} vg

ADVM-043 at 4×10^{14} vg

ADVM-043 at 1.2×10^{15} vg

ADVM-043 at 4.8×10^{15} vg

[REDACTED]

All 4 dose levels for Cohorts 1 through 4 remain below the NOAEL and are expected to be safe, based on the findings from Study ADVM-1701.

[figure not shown]
To date, over 100 clinical trials utilizing AAV driven gene therapy have been conducted (<https://www.wiley.com/legacy/wileychi/genmed/clinical/>). Multiple studies have used or are using similar doses to those being explored in this study. In one such study, doses up to 5.0×10^{12} vg/kg of liver-directed gene transfer for hemophilia B employing the AAVrh.10 vector (AAVrh.10FIX) were found to be generally well tolerated. (Dimension Therapeutics 2017). In a separate hemophilia A study conducted by BioMarin, the dosing of AAV5 (BMN 270) at 6×10^{13} vg/kg (approximately 4.6×10^{15} vg/subject based on the median weight) in 7 subjects has been shown to be safe and well-tolerated, and to produce durable and therapeutic FVIII levels out to 78 weeks (Biomarin 2017). BioMarin is currently conducting a global Phase 3 study in up to 40 subjects with hemophilia A with BMN 270 at 6×10^{13} vg/kg (ClinicalTrials.gov: NCT03370913 2018).

In ADV-043-01, four dose levels have been selected to find a safe dose with the potential to show a meaningful effect in achieving plasma A1AT concentrations at or above the therapeutic target of 0.57 mg/mL (approximately 11 μ M) that could potentially benefit patients with progressive lung disease. At the same time, we want to minimize patient exposure to sub-therapeutic doses of ADV-043 and therefore have selected as low as 2 subjects per cohort (Section 3.3). Normal human A1AT (M-A1AT) levels range from 1.09 to 2.61 mg/mL (20 to 50 μ M).

[REDACTED] A starting clinical dose of [REDACTED] is projected to result in protein expression levels of approximately 0.04 to 0.1 mg/mL of M-A1AT in humans and that the highest dose of [REDACTED] may potentially reach approximately 2.4 to 6.0 mg/mL of M-A1AT in humans if the protein expression between mice and humans was equivalent.

Prior gene therapy studies have shown marked reduction in protein expression levels by four-fold or greater when comparing preclinical mouse studies to human trials (Bunting 2018; Nathwani, Rosales, et al 2011). As such, the primary objective of Cohort 1 is to establish an acceptable safety profile before proceeding to Cohorts 2 through Cohort 4. Given that AAVrh.10 and AAV8 have similar properties (both belong to Clade E family and differ by only 8% in their amino acid sequence (Wang, Bell, et al 2015), based on the protein expression results published by Nathwani employing AAV8, a 10-fold difference in expression may be reasonably predicted from mouse to human. If so, then the dose proposed in Cohort 4 may achieve up to ~0.6 mg/mL (~11 μ M) protein expression, which would overlap with the minimum target therapeutic levels of total A1AT protein for patients with A1AT deficiency.

The Sponsor and the DMC will be reviewing the ongoing safety and protein expression data (as appropriate) from each Cohort prior to making the decision to dose escalate to the next dose level cohort.

